be regarded as treatment-emergent. For medications, the medication will be classified as concomitant.

- If the onset/start date is completely missing then the onset/start date will be imputed to the date of first dose of study treatment and therefore, for AEs, the event will be regarded as treatment-emergent and, for medications, the medication will be classified as concomitant.

The following rules will be applied to partial end/stop dates:

- If only the month and year are specified, then the last day of the month will be used;
- If only the year is specified, then December 31 of the known year will be used;
- If the stop date is completely unknown, the stop date will not be imputed.

Note that the start date or stop date of a prior medication (partial or otherwise) should not be imputed past the Screening date - 1.

In addition to onset and stop dates, the onset and end times of AEs occurring on the day of infusion will be collected on the eCRF. Onset and end times may also be recorded for other AEs that do not occur on the same day as the infusion. The duration of AEs with onset and end times will be calculated in days and hours:minutes (hh:mm) as:

$$\text{Duration of AE} = \text{End Date and Time} - \text{Onset date and time}$$

In cases where only the onset and stop dates are recorded for an AE, the duration of an AE will be calculated in days as:

$$\text{Duration of AE} = (\text{Stop Date} - \text{Onset Date}) + 1$$

Note that for participants who have an AE which starts and stops on the same day, but with only a start time or only a stop time recorded, it will be assumed that their AE started from 00:00 (if no start time is recorded) and ended at 23:59 (if no stop time is recorded) on that day.

If the date of a participant's initial diagnosis is incomplete, it will be imputed to the most recent feasible date for the calculation of time since initial diagnosis as follows:

- If only the day is missing, it will be imputed to the last day of the known month;
- If the day and month are missing, it will be imputed to December 31 in the known year;
- If the date of initial diagnosis is completely missing, then time since initial diagnosis will not be calculated.

The above date imputation rules will be applied to partially missing stop dates of a participant's last prior anti-cancer systemic therapy as well as partially and completely missing dates of progression/relapse on last prior anti-cancer systemic therapy.

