- Best response to the most recent prior anti-cancer therapy regimen
- Number of prior anti-cancer systemic therapy + radiotherapy regimens (0, 1, 2, 3, >3)
- Best response to the most recent anti-cancer systemic therapy + radiotherapy regimen
- Reasons for discontinuation of the most recent line^[a]
- Time from completion of most recent line^[a] to the start of study treatment (<1 month, 1-<3 months, 3-6 months, >6 months)^[b]
- For participants that progressed after their most recent line^[a], the time from progression to the start of study treatment (<1 month, 1-<3 months, 3-6 months, >6 months)^[b]
- Number of prior anti-cancer radiotherapies (including radiotherapies given alone and concurrently with anti-cancer systemic therapy) (0, 1, 2, >2)
- Number of prior anti-cancer surgeries and procedures (0, 1, 2, >2)

^[a] Most recent line is the last prior anti-cancer therapy regimen received which may be a prior anti-cancer systemic therapy given alone or concurrently with radiotherapy.

^[b] 1 month = 30 days.

Time from completion and time from progression relative to the last line of anti-cancer systemic therapy will also be summarized using frequency counts and percentages as well as summary statistics.

The number and percentage of participants with any prior anti-cancer systemic therapy, and any prior anti-cancer systemic therapy given concurrently with radiotherapy will be summarized for the SS by treatment group and for all participants, and by WHODD Anatomical Main Group [Level 1 term text], Pharmacological Subgroup [Level 3 term text] and PT.

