6.4 Cancer status at Screening

The current cancer status of study participants at entry into Part A of this study will be assessed at the Screening visit and listed for the ES. This listing will include tumor type, T, N and M classifications and TNM stage, Duke's score and Gleason score (if relevant to the tumor type),

histological and cytological diagnosis details (as relevant), whether the participant has any metastases and associated anatomical location, whether the tumor is recurrent and whether the participant had relapsed from their last line of anti-cancer therapy.

Tumor type, TNM classifications and stage, Duke's score, Gleason score, presence of metastases and anatomical location of metastases, and time since relapse on last line of therapy (calculated in days using the date of the Screening visit and date of relapse) will be summarized by treatment group and for all study participants based on the SS. In the summaries of categorical variables, percentages will be calculated based on the number of study participants with non-missing data. Further, for the cM0(i+) M classification, Duke's score and Gleason score, the denominator for the percentage calculation will be the number of study participants for which these assessments are applicable (since they only apply to certain tumor types).

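### Partial diagnosis and progression/relapse dates are imputed to month-end or 31 December with no cap at Screening, so some baseline times come out zero or negative (minor)

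*SAP*

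**What the plan says.** Section 4.2.3 of the Part A SAP introduces its rule for an incomplete diagnosis date with a sensible aim: "it will be imputed to the most recent feasible date for the calculation of time since initial diagnosis as follows". Two fixed substitutions follow: "If only the day is missing, it will be imputed to the last day of the known month" and "If the day and month are missing, it will be imputed to December 31 in the known year". The section then extends these rules to partial stop dates of the last prior systemic therapy, "as well as partially and completely missing dates of progression/relapse on last prior anti-cancer systemic therapy".

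Three nearby sentences deal with limits:

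- "Note that the start date or stop date of a prior medication (partial or otherwise) should not be imputed past the Screening date - 1". This concerns medication dates only.
- Where the stop date or progression date of the last prior systemic therapy is wholly unknown, Screening date - 1 is used.
- Partial dates are not to be set equal to the first-dose date.

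The resulting times are used in three places. Section 6.2 measures time since diagnosis back from the Screening visit, in months. Section 6.4 summarizes time since relapse, "calculated in days using the date of the Screening visit and date of relapse". Section 6.3 summarizes "the time from progression to the start of study treatment", both in categories (the lowest being under 1 month, with 1 month taken as 30 days) and by summary statistics. The Part A1 SAP has the same rules in 4.4.1 and the same uses in 6.2 to 6.4.

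**The concern.** The substitutions do not carry out the aim that introduces them. A diagnosis or relapse recorded as history at Screening cannot have happened after Screening. Yet a date known only to the Screening month is moved to the end of that month, and one known only to the Screening year is moved to 31 December.

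None of the three limiting sentences closes the gap. Diagnosis and progression are not medication dates; the Screening date - 1 rule needs a completely missing date; and not using the first-dose date does not prevent a later one. The rules are therefore inconsistent for these dates: a wholly unknown progression date lands before Screening, while one known to lie in the Screening month or year lands on or after it.

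At stake are the continuous baseline summaries. Treatment groups are small (3 to 6 evaluable participants per Part A cohort, up to 8 per Part A1 cohort), so one impossible value can dominate a mean or minimum. Because imputed dates are not shown in listings, the date behind such a value would not appear there.

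**Working it through.** The SAPs give no figure to reproduce. The check applies the rules literally by date arithmetic.

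**Inputs.** The imputation rules are from 4.2.3 (Part A) and 4.4.1 (Part A1); the reference dates are from 6.2, 6.3 and 6.4; the Screening Period of up to 28 days is from 3.2.2. My assumptions are an example calendar year (2022) and a first dose 7, 14 or 28 days after Screening.

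**Formulas.** Time to Screening = Screening date - imputed date (multiplied by 12/365.25 for months). Time to first dose = first-dose date - imputed date.

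**Example: Screening on 10 June 2022.**

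| Date known as | Imputed to | Days to Screening | Months | Days to first dose at 7 / 14 / 28 days |
|---|---|---|---|---|
| June 2022 | 30 June 2022 | -20 | -0.66 | -13 / -6 / +8 |
| 2022 | 31 December 2022 | -204 | -6.70 | -197 / -190 / -176 |
| Either, capped at Screening - 1 | 9 June 2022 | +1 | +0.03 | +8 / +15 / +29 |

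**All 365 Screening days of the example year, time to Screening (6.2 and 6.4).**

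- Date in the Screening month: negative on 353 days, zero on 12 (Screening on the last day of a month), never positive; minimum -30 days.
- Year-only date in the Screening year: negative on 364 days, zero on 1, never positive; minimum -364 days.

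**The same 365 days, time to first dose (6.3).** Zero or negative for first dose 7, 14 and 28 days after Screening:

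- Month known: 281, 197 and 29 days. For the first two, 365 - 12 x 7 = 281 and 365 - 12 x 14 = 197. For 28 days, 7 x 3 + 4 x 2 = 29.
- Year only: 365 - 7 = 358, 365 - 14 = 351 and 365 - 28 = 337 days.

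**Effect on a small cohort (illustration).** Take six participants, five of them at +30 days from progression to first dose, and the sixth the example participant dosed 14 days after Screening.

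- Year-only date: (5 x 30 - 190)/6 = -6.7 days.
- Month-known date: (5 x 30 - 6)/6 = 24.0 days.
- Either date, capped: (5 x 30 + 15)/6 = 27.5 days.

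**Category check (6.3).** With the cap, the largest possible time to first dose is 28 + 1 = 29 days, below the 30-day month. Without it, the time is at most 28 days. If negative values are counted in the lowest category, the category is the same either way.

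**How often, given a partial progression date.** The SAPs give neither the rate of partial dates nor the interval from progression to Screening. Suppose that interval is uniform on 1-60 days (range 1-30 to 1-90). The share of month-known dates giving a non-positive time since relapse is the sum over lags L = 1 to 30 of (30.4 - L)/30.4, about 14.7, divided by the interval length: 24% (49% to 16%). For year-only dates it is 1 minus mean lag/365: 1 - 30.5/365 = 92% (96% to 88%). These are shares of partial dates, not of participants.

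**The case against.** The best defence is that the intent is plain. The lead-in asks for a feasible date, a post-Screening date for a history item is not feasible, and Screening date - 1 is already used twice in the same section. A careful programmer might cap the date unprompted, and an impossible minimum would probably be noticed at a Data Evaluation Meeting. This supports a low severity. It does not remove the point, because the substitutions are stated as the way to reach the aim and, followed as written, they miss it.

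Other limits also stand. An initial diagnosis both incomplete and within the Screening month or year should be rare in recurrent or metastatic disease, so progression/relapse is the case that matters. A recent progression recorded by year alone is also unlikely, so the largest negative values are the least likely ones.

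Three stronger readings are tempting, and the documents support none of them:

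- *All three times always become zero or negative.* This is true for 6.2 and 6.4. The 6.3 time runs to first dose and can stay positive; for a month-known date and first dose 28 days after Screening it does so on 336 of 365 days.
- *The under-1-month category is inflated, so the population looks more recently progressed.* The category is the same with and without the cap. Leaning towards recent dates is also the plan's stated choice.
- *A partly known date is in general handled worse than an unknown one.* This holds only for the Screening month or year. A partial date in an earlier month or year still falls before Screening and carries more information than Screening date - 1.

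**Conclusion.** The gap is real and minor. Under the rules as written, a partial diagnosis or progression/relapse date in the Screening month, or a year-only date in the Screening year, always gives a zero or negative time since diagnosis (6.2) or since relapse (6.4). Time from progression to first dose (6.3) may be zero or negative as well, depending on the gap between Screening and dosing. The treatment of completely missing progression dates is inconsistent with this.

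The effect is confined to the continuous descriptive baseline summaries (mean, median, minimum), mainly for progression/relapse. No safety or antitumor endpoint is affected. A reader might infer from the conditional shares above that the problem will be common, but the SAPs give no rate of partial dates, so its frequency is unknown. The stop date of the last prior systemic therapy is left out of this point because the prior-medication limit may already cover it.

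**What to change.** Add to Section 4.2.3 of the Part A SAP and Section 4.4.1 of the Part A1 SAP: *If the imputed date of initial diagnosis or of progression/relapse is on or after the Screening date, Screening date - 1 will be used.* This is the bound both sections already apply to neighbouring cases. It removes every zero or negative value in 6.2, 6.3 and 6.4 that arises from these imputations. The cost is one sentence per SAP and a minimum function in the derivation; no data collection, table shell or endpoint changes.

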4.2.4 Impact of COVID-19

The FDA and European Medicines Agency (EMA) have provided guidance (see references listed in Section 12) to help assure the safety of all trial participants, maintaining compliance with good clinical practice (GCP), and minimizing risks to trial integrity during the COVID-19 pandemic. At the time of writing this SAP, the impact of the pandemic is still evolving and regulators continue to clarify their position, and how to handle missing or delayed assessments resulting from the pandemic is part of the risk assessment of the impact of COVID-19 on trial integrity. For this purpose, the impact at a visit level will be assessed by data collected on a specific COVID-19 impact eCRF form and protocol deviations related to COVID-19. Due to the timing of the start-up of recruitment of participants into this study, the consequences for Part A are not expected to be significant and, as a result, no details on strategies for handling missing data are included in this version of the SAP. However, should the ongoing review of COVID-19-related protocol deviations suggest that the impact is more significant than expected, e.g. in the case of a second wave, the SAP may be updated to include further details of handling missing data and/or any sensitivity analyses required. Note that there are no guidelines regarding how much missing data is too much, and there is no proportion of missing data under which valid results and preservation of study power can be guaranteed. In accordance with the EMA guidance, an independent Data Monitoring Committee (DMC) may be convened to make an assessment regarding the scientific integrity of the study.

4.3 Handling of repeated and unscheduled measurements

All repeated and unscheduled measurements will be presented in the data listings, where applicable. Repeated measurements are defined as more than 1 measurement at the same timepoint. For example, the same laboratory parameters assessed twice using the same batch of blood samples due to issues with the first assessment. The following general rules will apply to all repeated and unscheduled measurements:

- Unscheduled and repeated measurements prior to the first dose of study treatment will be used in the determination of Baseline and hence in the calculation of summary statistics at Baseline;
- Unscheduled and repeated measurements performed after the first dose of study treatment will not be included in the calculation of change from Baseline, summary measures such as minimum, maximum, average and last post-Baseline value calculated for the summaries of laboratory data (see Section 8.3), vital signs (see Section 8.4.1) and 12-lead ECG (see Section 8.4.2), or summary statistics, i.e. only the scheduled measurements will be used and summarized. Similarly, only scheduled visits will be used in the summaries of shifts from Baseline to the worst post-Baseline CTCAE severity grade for laboratory data (see [Section 8.3](#)).
- For the summaries of the investigator's overall tumor response assessment, protocol-defined windows will be applied to all post-Baseline tumor assessments (scheduled or

unscheduled, but excluding tumor assessments performed at the SFU visit), as detailed in Section 10.1.2. Those tumor assessments which fall outside of the window will be considered as unscheduled assessments and not included in the summaries.

- Best overall response, DOR and PFS derivations will use data from all scheduled and unscheduled tumor assessments.
- All data from unscheduled visits will, however, be included on the relevant data listings.

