2.3 Study design and conduct

Study ONC001 is a multicenter, nonrandomized, open-label, Phase 1/2 study evaluating the safety, PK, efficacy (as assessed by antitumor activity), PD, biomarkers, and immunogenicity (ADA activity) of intravenous (iv) UCB6114 as monotherapy and in combination with selected standard of care (SoC) regimens in study participants with advanced solid tumors.

The study has a modular design including up to 3 dose escalation modules (Parts A, B, and C), 1 dose adaptation module (Part A1), and up to 4 dose expansion modules (Parts D, E, F, and G). Depending on emerging data, not all modules may open. This SAP is focused only on the first dose escalation module of the study (Part A).

[figure not shown]
Part A consists of a Screening Period (28 days), a Treatment Period (consisting of 28-day cycles), an SFU visit (approximately 30 days after the last dose of study treatment) and a Final Visit (approximately 3 months after the last dose of study treatment). The planned duration of study treatment is 2 cycles. Participants may remain on study for additional cycles if they are receiving therapeutic benefit or until they fulfill one of the criteria for study discontinuation.

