3.2.2 Study periods

Part A of the study will consist of the following study periods:

- Screening Period – up to 28 days;

- Treatment Period – Successive 28-day cycles of study treatment (Q2W dosing on Day 1 and Day 15 of each cycle continuing until disease progression, unmanageable toxicity, or participant withdrawal). Within the first cycle of the Treatment Period, a 28-day DLT Observation Period is defined to determine safety events for dose escalation decisions. If a study participant is a sentinel participant in the cohort, there is an initial DLT Observation Period of 16 days, after which the cohort may be opened for further enrollment;
- Safety Follow-up Period – up to 30 days after the last dose of study treatment.

There will be a further extended follow-up period, up to 3 months after the last dose of study treatment, at which time the Final Visit will be performed.

For each participant, the end of the Treatment Period is defined by the date of their last dose of study treatment.

The end of Part A of the study is defined by the date of the Final Visit for the last participant (3 months after the last participant's last dose of study treatment), or the date of the SFU visit, if they discontinue prior to attending the Final Visit, or their last contact date if they discontinue early from the study without attending the SFU visit.

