8.1 Extent of exposure

Details on study treatment administration on Day 1 and Day 15 of each cycle of study treatment will be listed. This listing will be split into two parts. The first part will include the start and stop dates and times of infusion, duration of infusion, infusion rate, whether the infusion was temporarily stopped/interrupted, whether the infusion was permanently discontinued and, if this was the case, whether the interruption or permanent discontinuation was due to an AE or other reason. The second part of this listing will include, for each visit, infusion site, total volume delivered, volume infused, planned total dose and total dose actually administered at infusion. In addition, the percentage of planned dose received, total dose administered across all cycles, the number of complete cycles of study treatment received and the total number of doses of study treatment received will be listed.

The percentage of planned dose received will be calculated for each study participant at each dosing visit within each cycle as follows:

$$\text{Percentage of Planned Dose Received} = 100 \times \frac{\text{Total Dose Administered}}{\text{Planned Total Dose}}$$

Actual duration of infusion will be calculated in minutes only for those study participants who did not have any temporary interruption(s) of their infusion using the infusion start and stop times and included on this listing. Length of interruption(s) will be calculated for those study participants who had temporary interruption(s) of their infusion.

Extent or duration of exposure will be calculated and summarized. Frequency counts and percentages for the number of complete cycles of study treatment received (1, 2, 3, 4, >4) and summary statistics for the total dose of study treatment received across all cycles, the total number of doses of study treatment received and the duration of exposure to study treatment will be presented.

Duration of exposure will be calculated in days as follows:

$$\text{Duration of Exposure} = (\text{Date of Last Dose} - \text{Date of First Dose}) + 30$$

Note that 30 days is added to this calculation to account for a participant's continued exposure to UCB6114 following their last dose of study treatment.

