8.2 Adverse events

The primary safety endpoints for Part A of this study are the incidence and severity of TEAEs (including SAEs) from the first dose of study treatment on Day 1 of Cycle 1 until the end of the SFU Period (up to 30 days following the last dose of study treatment), and the incidence of DLTs from the first dose of study treatment on Day 1 of Cycle 1 until the end of the DLT Observation Period (Day 28 of Cycle 1).

All AEs in Part A of the study will be coded using MedDRA® and classified as pre-treatment and treatment-emergent relative to the first dose of study treatment. Adverse events with a start date prior to the first dose of study treatment will be defined as pre-treatment AEs. A TEAE is defined as any AE with a start date on or after the first dose of study treatment up until the last dose of study treatment + 30 days. A pre-treatment AE which increases in severity on or after the first dose of study treatment will also be counted as a TEAE. Note that in this case, the pre-existing AE will have a stop date and an outcome of 'worsened' and a new AE (with the same verbatim) will be entered with the same start date and the increased severity recorded on the eCRF. Any AE (including SAEs) with an onset date later than the last dose of study treatment + 30 days will not be considered as treatment-emergent and therefore will not be included in the tabulations of TEAEs. These AEs will be considered as post-study AEs and will be listed only. Where onset dates are missing or partially missing, AEs will be assumed to be treatment-emergent, unless there is clear evidence to suggest that the AE started prior to the first dose of study treatment and it has not increased in severity. Missing or partially missing dates for AEs

will be handled as described in [Section 4.2.3](#). All AEs for a participant will be recorded in the eCRF from the time of informed consent until completion or early discontinuation of Part A of this study. Serious adverse events are to be reported up to 30 days after the Final Visit (i.e. up to 150 days after the last dose of study treatment).

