Observed values and changes from Baseline in the hematology, serum chemistry and coagulation parameters presented below in Table 8-1 will be summarized at each visit. In addition, for each of these parameters, the Baseline value, the minimum, maximum, average and last post-Baseline value for each participant will be summarized by cycle using descriptive statistics. These post-Baseline summary measures will be calculated based on all available scheduled postdose values within each cycle, i.e. from Day 8 of the current cycle up to Day 1 (predose) of the subsequent cycle. The last value in a cycle will be the predose value of the subsequent cycle where a subsequent cycle occurs, otherwise it will be the value at the last scheduled assessment. If only 1 value is available then the average will not be calculated and presented but this value will be used for the minimum, maximum and last post-Baseline summary measures. These summary measures for each cycle will also be listed.

For those laboratory parameters with a CTCAE toxicity assigned, shift tables for the change from Baseline in CTCAE severity grade at each visit and to the worst post-Baseline CTCAE severity grade during the Treatment Period will be presented.

This document cannot be used to support any marketing authorization
application and any extensions or variations thereof.

Table 8-1: Clinical Laboratory Assessments

Laboratory Assessment	Laboratory Parameters
Hematology	Platelet Count, RBC Count, Hemoglobin, Hematocrit, RBC Indices (MCV, MCH, MCHC), WBC Count with Differential (Absolute Neutrophils, Absolute Lymphocytes, Absolute Monocytes, Absolute Eosinophils, Absolute Basophils)
Clinical Chemistry	ALT, AST, ALP (including liver-specific ALP for use in assessing participants with bone metastases at Screening), Bicarbonate, Sodium, Potassium, Magnesium, Chloride, Calcium, Total Bilirubin, BUN or Urea, Serum Creatinine, Glucose (non-fasted), Phosphorus or Phosphate, Albumin, Total Protein, Uric Acid, Amylase, GGT, Cholesterol, Creatine Kinase, CRP, LDH, Lipase, Triglycerides
Coagulation	aPTT and either PT or INR
Routine Urinalysis	Specific Gravity, pH, Glucose, Protein, Blood, Ketones, Bilirubin, Urobilinogen, Nitrite, Leukocyte Esterase by Dipstick Microscopic Examination (if blood or protein is abnormal, including crystals)

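### Part A: the worst laboratory grade and per-cycle minimum/maximum leave out unscheduled results, and the worst-grade table also stops at the last dose, so these supportive summaries can only understate extremes

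*SAP*

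**What the plan says.** Four rules in the Part A SAP act together.

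- **Unscheduled data, extremes.** Under Section 4.3, unscheduled and repeated measurements after the first dose "will not be included in the calculation of change from Baseline, summary measures such as minimum, maximum, average and last post-Baseline value"; the sentence covers laboratory data, vital signs and ECG. Section 8.3 repeats the rule for the laboratory summary measures, which are "calculated based on all available scheduled postdose values within each cycle". Sections 8.4.1 and 8.4.2 use scheduled post-dose values in the same way.
- **Unscheduled data, worst grade.** Section 4.3 adds that "only scheduled visits will be used in the summaries of shifts from Baseline to the worst post-Baseline CTCAE severity grade for laboratory data".
- **Window of the worst grade.** Section 8.3 plans shift tables at each visit and "to the worst post-Baseline CTCAE severity grade during the Treatment Period will be presented".
- **End of that window.** Section 3.2.2 states that for each participant "the end of the Treatment Period is defined by the date of their last dose of study treatment".

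Two other sections look further ahead. Section 8.2 counts adverse events as treatment-emergent "up until the last dose of study treatment + 30 days". Section 8.1, on duration of exposure, says that "30 days is added to this calculation to account for" continued exposure after the last dose.

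**The concern.** Restricting by-visit means and changes to scheduled values is sound, because each visit then has a comparable set of results. An extreme is a different kind of statistic. Unscheduled samples are often taken because something looks abnormal, so a rule that drops them removes results that may well be the worst.

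Section 4.3 is also uneven. Unscheduled and repeated values before the first dose are used to define Baseline, and unscheduled tumor assessments are used for best overall response, duration of response and PFS. Post-dose safety extremes are denied the same completeness.

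The cut at the last dose adds a second gap, and it is proportionally largest in participants who stop early, some of whom may stop for toxicity. At stake is how far a table labelled as worst post-Baseline can be trusted as support for the primary objective of Part A, the safety profile. Cohorts have 3 to 6 evaluable participants, so one missed participant is visible in any incidence.

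**Working it through.** The SAP states no figure that depends on these rules, so there is none to reproduce. The check is on direction and on days covered.

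**1. Direction.** Let S be the valid scheduled post-dose results and U the valid unscheduled ones. Then max(S) ≤ max(S and U together), and min(S) ≥ min(S and U together). A worst grade taken from S alone is at or below the worst grade from all results. The error has one sign.

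**2. Window.** Inputs: doses on Days 1 and 15 of 28-day cycles (Section 2.3); "The planned duration of study treatment is 2 cycles", hence 4 doses; worst-grade window ending at the last dose (Sections 8.3 and 3.2.2); TEAE window ending 30 days later (Section 8.2).

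- Day of last dose after k doses = 14(k − 1) + 1
- End of TEAE window = day of last dose + 30
- Share not covered = 30 / end of TEAE window

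| Doses | Last dose | TEAE window ends | Not covered |
|---|---|---|---|
| 1 | Day 1 | Day 31 | 30/31 = 96.8% |
| 2 | Day 15 | Day 45 | 30/45 = 66.7% |
| 4 (planned) | Day 43 | Day 73 | 30/73 = 41.1% |
| 8 | Day 99 | Day 129 | 30/129 = 23.3% |

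These are calendar days, not numbers of laboratory results.

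**3. One dose only.** The worst-grade window ends on Day 1. Baseline is the predose value of that day (Section 3.3), and Section 8.3 starts the post-dose laboratory values of a cycle at Day 8. No qualifying post-Baseline value falls inside the window.

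**4. Weight of one participant.** 1/3 = 33.3 percentage points in a cohort of 3, and 1/6 = 16.7 in a cohort of 6.

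**5. Illustration on assumed values.** Suppose the true rate of Grade 3 or higher laboratory values is p = 20%, and a share q of those worst values is seen only unscheduled or after the last dose. The chance that a cohort of n shows at least one is 1 − [1 − p(1 − q)]^n.

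| n | q = 0 | q = 25% | q = 50% |
|---|---|---|---|
| 6 | 73.8% | 62.3% | 46.9% |
| 3 | 48.8% | 38.6% | 27.1% |

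The SAP gives neither p nor q, and the conclusion does not rest on this table.

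**The case against.** The strongest reply is that little is hidden. Unscheduled results are listed (Section 4.3), and out-of-range laboratory values have their own listing (Section 8.3). Grade shifts are tabulated at each visit, and SFU data are summarized (Section 4.4). A clinically significant abnormality reported as an AE enters the TEAE tables. The primary endpoints are TEAEs and DLTs; laboratory, vital-sign and ECG data are supportive. The SMC reviews all safety data under separate output specifications (Section 4.5), so no dose decision is shown to depend on this table. In cohorts this small, reading listings is realistic.

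All of that stands and limits the severity. It does not answer the point: none of these outputs gives the participant-level worst grade, and AE reporting depends on the investigator's judgment.

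A reader might infer more than the document supports:

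- **That the safety summaries as a whole omit these results, or that a transient Grade 3 or 4 value vanishes.** It does not; the outputs just named can still show it.
- **That minimum and maximum also stop at the last dose.** They do not. Section 8.3 follows a cycle to the next predose value or, if no cycle follows, the last scheduled assessment.
- **That 41% of laboratory results are lost.** The figure counts days. The laboratory visit schedule is not in the Part A SAP, and for the planned two cycles the loss among scheduled draws may be as little as the SFU sample, which by-visit tables already carry.
- **That the worst-grade and TEAE tables would agree if the windows matched.** One uses programmed grades and the other investigator-assigned grades, so they can differ anyway.
- **That Part A1 has the same defect.** Its Section 4.5 repeats the worst-grade sentence, but its Section 8.3 plans shifts only at each visit, and it plans no per-cycle minimum or maximum.

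**Conclusion.** The point holds for Part A, as something that should be fixed. The worst post-Baseline laboratory grade, and the per-cycle minimum and maximum for laboratory data, vital signs and ECG, are built from scheduled values only and can err only towards milder extremes. The worst-grade table also leaves out the 30 days after the last dose: 30 of 73 calendar days for the planned four doses, rising to 30 of 31 after a single dose, where the table holds no qualifying value.

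The day counts assume dosing on schedule and the definition of the Treatment Period as written in Section 3.2.2. How many results are affected cannot be known from the document, since it gives no rate of unscheduled high-grade values. The affected outputs support the primary safety objective and are not the primary endpoints, so the point stops short of must-fix.

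**What to change.** **Part A SAP, Sections 4.3, 8.3, 8.4.1 and 8.4.2:**

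1. Derive the worst post-Baseline CTCAE grade from all valid results after the first dose, scheduled and unscheduled, through last dose + 30 days. State that window in Section 8.3 instead of referring to the Treatment Period.
2. Derive the per-cycle minimum and maximum for laboratory data, vital signs and ECG from all valid scheduled and unscheduled post-dose results.
3. Where a repeat replaces a faulty assay, use only the valid result. Section 4.3 itself gives problems with the first assessment as an example of why repeats arise.
4. Keep scheduled-only data for by-visit summaries, including the by-visit liver-abnormality, QTcF and TEMA tables.

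**Part A1 SAP, Section 4.5:** delete the worst-grade sentence, which has no matching output in Section 8.3. If that table is intended, add it there under the same rule.

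The cost is SAP wording and a change to record-selection flags in the analysis datasets. The data are already collected and listed.
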